COVER PAGE

Official Title: Treatment of Chronic Antibody-mediated Rejection in
Kidney Transplant with Acthar

ID HP-00063872

NCT02546492

Date of the Document: 21JUN2016

Questcor Clinical Investigator Initiated Study (IIS) Proposal Guidelines

| | | |
|-------------------------------------|---|--|
| Study Title: | Treatment of Chronic Antibody-mediated Rejection in Kidney Transplant with Acthar | |
| Protocol Version and Date: | | |
| Principal Investigator (PI): | [name], MPH | |
| PI Contact information: | [contact] | Email: [contact] |

A. SPECIFIC AIMS

Use of Acthar for treatment of chronic antibody-mediated rejection in kidney transplant recipients is safe and associated with improved graft outcome

B. BACKGROUND AND CLINICAL SIGNIFICANCE

Chronic antibody-mediated rejection (CAMR) is the clinico-pathological manifestation of chronic active graft injury as a result of donor-directed antibody. This type of graft injury is the major cause of graft failure after the first year of transplantation. The dominant histological manifestation of this process is transplant glomerulopathy (TG), characterized by double contours in more than 10% of glomerular capillary loops. Gloor JM et al observed that among indication and protocol biopsies, 9.5% of the patients had TG at a median of 21±14 months (range 4-61) after transplant. It could also present as peritubular capillary basement membrane multilayering, interstitial fibrosis/tubular atrophy, and/or fibrous intimal thickening in arteries. CAMR is strongly and independently associated with poor graft survival. In the study by Gloor et al, mean graft survival after the diagnosis of TG was 43±7 months. We examined the outcome in 145 patients with TG at our center (unpublished data). Graft survival at 66 months of diagnosis was only 10%. The role of donor-specific alloantibody (DSA) in pathogenesis of graft injury in CAMR has been clearly demonstrated. Through complement dependent and independent mechanisms, the antibodies cause phenotypic changes in endothelial cells (EC). Inflow of inflammatory cells, especially monocytes ensue, and with ongoing EC injury, diminished patency of the capillary loops and progression to reduplication of the glomerular basement membrane occurs. Our group has shown the strong association of glomerular CD 68-positive cells. (macrophages) with TG, and as the only independent predictor of graft survival. The clinical manifestation of CAMR is generally insidious and non-specific, consisting of proteinuria, unexplained loss of allograft function, and hypertension. Unfortunately, there is no specific therapeutic regimen for this major cause of graft failure. The role of Melanocyte stimulating hormone (MSH) receptors in suppressing inflammation through downregulation of the lymphocytes, macrophages, PMNs and eosinophils, and their role in protecting the glomerular endothelial cells and podocytes, provide a strong rationale for use of Acthar in treatment of CAMR. We have hypothesized that Acthar therapy in patients with CAMR is safe and delays the resultant graft injury. We propose to conduct an open-label, uncontrolled, pilot prospective cohort study using Acthar as a part of immunosuppressive regimen for patients with clinical/histological diagnosis of CAMR.

C. RESEARCH DESIGN AND METHODS

Study Type/Design

This is an open label safety and feasibility trial using Acthar® in addition to our center-specific standard therapy, which could include increase in maintenance immunosuppression, high dose IVIG (2 g/Kg), and/or Rituximab, in patients with CAMR.

The inclusion criteria include:

- Age >18 years
- Morphologic diagnosis of CAMR, by light &/or electron microscopy any time after transplantation
- eGFR>25 ml/min

The exclusion criteria include:

- Diagnosis of malignancy within a year prior to enrollment (except cured cutaneous basal cell or squamous cell carcinoma).
- Lack of evidence of antibody involvement
- Pregnancy, lactation, or refusal to use birth control in women of child bearing potential
- Active infection, or history of HIV
- History of liver or thoracic transplant

Endpoints

The **efficacy primary endpoint** of the study is the composite of graft loss, death, decrease in eGFR>10%, and increase in proteinuria, defined by >50% increase if baseline proteinuria <2 g, or persistence of proteinuria >2 g otherwise, at one year after initiation of the treatment. The **safety endpoints** include the serious adverse events during the study period attributable to study drug.

Secondary end-points:

- 1- Death
- 2- Graft loss (defined as return to dialysis or retransplantation)
- 3- Decrease in eGFR>10% at 1 year
- 4- Increase in proteinuria >50% if baseline proteinuria<2 g, or persistence of proteinuria >2 g otherwise
- 5- Persistence of DSA, by number of antibodies and related MFI
- 6- g and cg scores in the biopsies, maximum number of glomerular CD68+ cells; severity of interstitial fibrosis/tubular atrophy

Patient Recruitment

The study will be conducted in renal transplant recipients with histological diagnosis of chronic AMR at any time after transplantation with fairly preserved graft function. We are planning to enroll 20 patients with histological diagnosis of CAMR.

Treatment Overview Screening protocol, concomitant treatments, etc.

Dosage and Administration of Acthar

Subjects will receive Acthar® 40 units twice a week subcutaneously for 2 weeks. If the drug is well tolerated the dose will be increased to 80 units twice a week for another 22 weeks.

Dosage considerations in special circumstances, and based on the side effect profile of individual participants, the investigator may recommend a modified dose Acthar® as indicated below:

- 1) Patients with diabetes may be given Acthar® 16 units daily, instead of 80 units twice a week (with the aim of maintaining better glycemic control (Tumlin 2013))
- 2) Patients who develop side effects on the standard dose of Acthar® (40 units twice a week followed by 80 units twice a week) may be given a lower, tolerable dose of Acthar® either on a daily or a twice a week basis.

The patients will be maintained on their center-specific standard maintenance regimen, typically consisting of Tacrolimus,

Mycophenolate Mofetil/Sodium, and prednisone.

Patient Monitoring and Evaluation /Laboratory Testing and Study Schedule

After screening for the inclusion/exclusion criteria, the patients will be consented and enrolled in the study. The initial visit and subsequent study-related visits at 2, 4, 8, 12, 24, 36 and 52 weeks will include routine evaluation and physical examination and laboratory studies including CBC, electrolyte panel, eGFR, albumin, liver enzymes, and CNI/Sirulimus drug level, according to the center's standard of care. DSA will be tested at week 24, and 52 and patients will undergo a biopsy at week 52, as a part of our standard of care. The biopsies will be evaluated by light and electron microscopy using standard histological Banff criteria, and staining for CD68.

Potential Pitfalls and Contingencies Describe plans to address possible problems

We do not expect major problems with the treatment. It is not clear if treatment with Acthar will prevent or slow down the progression of CAMR. However, since there is no alternative therapy available, lack of response will not change the course of the disease process. There is a possibility that the patients could develop hyperglycemia; if so appropriate therapy will be provided.

Data Processing and Analysis

Statistical /Analytical Plan

The data will be collected on the variables listed above. Standard statistical methods will be used for description of primary and secondary endpoints. As a secondary analysis a historical cohort of patients with CAMR will be identified and graft survival in the study group will be compared with the historical cohort using survival analysis methods.

Sample Size Justification

The enrollment plan is not based on power calculation, as there is no previously successful treatment reported to use for sample size calculation. This is a cohort of reasonable size that is expected to provide invaluable data regarding the treatment effect, and provide data for power calculation for future studies.

D. REGULATORY, SAFETY AND MONITORING

After the initial visit the subsequent study-related visits will occur at 2, 4, 8, 12, 24, 36 and 52 weeks and will include routine evaluation and physical examination and laboratory studies as noted above for evaluation for efficacy and safety endpoints. The adverse effects will be reported to IRB and the sponsor, and patients with serious adverse effects resulting from the study drug, not amenable to medical therapy and those non-compliant with study protocol will be removed from the study. IND will be file with the FDA if the IRB requires it. The study protocol will be registered with Clinical trials.com

E. ESTIMATED DURATION OF THE STUDY AND CRITICAL TIMELINE ELEMENTS

I. Please complete expected/estimated dates:

| Table 1: Critical Timeline Elements | |
|--|-------------------|
| Element Name | Date |
| IRB approval, expected | 4-6 weeks |
| IND submission, expected | 6 weeks |
| Study start date, estimated | April 1, 2015 |
| Enrollment completion date, estimated | December 31, 2020 |
| Study completion date, estimated | December 31, 2021 |

II. Describe publication plan and anticipated number of abstracts and manuscript submissions (include intended conference(s) for presentation and month, year of conference(s)):

At one year and 2 years the interim analysis will be performed and the results will be submitted to national/international nephrology/transplant meetings, and at the completion of the study the final results will be submitted in the form of a primary manuscript reporting the primary efficacy and safety data, and secondary manuscripts reporting different secondary endpoints, as appropriate.

F. REFERENCES

R Ugarte, B. Kiangkitiwan, A. Haririan. Antibody-mediated rejection in kidney transplantation. 2014. 281-300. In M. Weir, E. Lerma (editors): *Kidney Transplantation, Practical Guide to Management*. Springer

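### The only named safety endpoint counts SAEs judged attributable to Acthar; without an all-cause SAE count beside it, a low figure cannot be interpreted

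*Combined protocol and SAP*

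**What the plan says.** Section C, Endpoints, states that the safety endpoints "include the serious adverse events during the study period attributable to study drug". No other safety endpoint is named. The same section lists death and graft loss in the efficacy composite and again as secondary endpoints, with no condition on cause.

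The setting for the attribution judgement is as follows:

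- Section B describes an "open-label, uncontrolled, pilot prospective cohort study".
- Section C, Study Type/Design, adds Acthar to the center's usual treatment, "which could include increase in maintenance immunosuppression, high dose IVIG (2 g/Kg), and/or Rituximab".
- The dosing part of Section C says patients are also "maintained on their center-specific standard maintenance regimen, typically consisting of Tacrolimus", mycophenolate and prednisone.
- Section C, Patient Recruitment: "We are planning to enroll 20 patients with histological diagnosis of CAMR".

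The Statistical/Analytical Plan says "Standard statistical methods will be used for description of primary and secondary endpoints" and does not mention the safety endpoint. The historical cohort is to be used for graft survival only. Section D has adverse effects reported to the IRB and the sponsor. It also removes from the study patients who are non-compliant, or who have serious effects judged due to the drug that medical therapy cannot manage. Section E promises safety data in the main paper.

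**The concern.** Safety is one of the two claims in the Specific Aims, and Study Type/Design presents the trial as one of safety and feasibility. The one safety endpoint it names has to pass through a causal judgement before an event counts. That judgement is made without blinding, in patients whose other drugs are themselves candidate causes, and with no group whose SAE rate could show what to expect without Acthar.

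If the endpoint is reported as written and nothing else is shown, a small number has two readings: few SAEs happened, or a good many happened and were assigned to other causes. The error can also run the other way, with background events blamed on Acthar because it is the new drug. At stake is whether a reader of the final paper can interpret the safety result at all. The validity of the trial is not in question.

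**Working it through.** **1. What is counted, by type of event.** Setting Endpoints, the Statistical/Analytical Plan and Section D side by side:

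| Event | Counted regardless of cause? | Where |
|---|---|---|
| Death | Yes | Efficacy composite; secondary endpoint 1 |
| Graft loss | Yes | Efficacy composite; secondary endpoint 2 |
| Other SAE, judged due to Acthar | Not applicable | Safety endpoint |
| Other SAE, judged not due to Acthar | No summary specified | Section D reporting may cover it; no analysis does |

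The gap is the last row: SAEs that are neither death nor graft loss and are judged unrelated.

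**2. Can attribution be checked against anything?** There is no concurrent control (Section B). The historical cohort serves the graft-survival comparison only (Statistical/Analytical Plan). So there is no SAE comparator.

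**3. Size.** The plan states no safety figure to reproduce, and its sample size is expressly not based on a power calculation. The only input is n = 20 (Patient Recruitment).

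- One patient moved across the attribution line changes the reported rate by 1/20 = 5 percentage points.
- If x patients have any SAE and k of them have one judged attributable, the endpoint reports k/20, where k can be any whole number from 0 to x.

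The documents give no SAE rate, so the values of x below are assumptions that show a range. Exact (Clopper-Pearson) limits are the 0.025 quantile of Beta(x, n − x + 1) and the 0.975 quantile of Beta(x + 1, n − x).

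| Assumed patients with any SAE | All-cause proportion (exact 95% CI) | Possible range of the attributed proportion |
|---|---|---|
| 0 | 0% (0 to 16.8%) | 0% |
| 2 | 10% (1.2 to 31.7%) | 0 to 10% |
| 4 | 20% (5.7 to 43.7%) | 0 to 20% |
| 8 | 40% (19.1 to 63.9%) | 0 to 40% |

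For zero events the upper limit is 1 − 0.025^(1/20) = 0.168.

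An attributed result of 0/20 is compatible with every row. The all-cause column separates the rows; the attributed count alone does not.

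**The case against.** The best defence is that the documents do not limit reporting to attributed events. The endpoint sentence uses the verb include, which leaves the list open. Section D sends adverse effects to the IRB and the sponsor without qualification, and ties causation to the drug only in the removal rule that follows. Section E promises safety data, not attributed events alone. The gravest outcomes, death and graft loss, are already counted whatever their cause. An event must also be identified before it can be attributed, so the records may already exist.

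Most of this stands. It narrows the gap to non-fatal SAEs without graft loss, and it means part of the remedy may only clarify what Section D already intends. It does not close the gap: reporting to an IRB is not an analysis, and no summary of SAEs regardless of cause is specified anywhere.

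Some stronger readings are tempting but unsupported:

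- A reader might infer that the plan intends to leave out unrelated SAEs, or that it will understate harm. The text shows an unspecified summary, and the direction of any error is unknown.
- A reader might treat the absence of a causality scale and a named assessor as an error in itself. It is missing detail; supplying it would not provide the missing comparator.
- A reader might take the wider spacing of visits after planned dosing ends as a sign of biased attribution. The documents do not say that SAEs are detected only at visits.

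**Conclusion.** The point holds as a cheap improvement to the safety summary. The plan names one safety endpoint, that endpoint depends on an unblinded judgement among competing causes, and there is no comparator for it. A low attributed count therefore cannot be told apart from many SAEs judged unrelated.

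The size of any error cannot be computed. What is certain is the step of 5 percentage points per patient at n = 20. The 0 to 40% range rests on an assumed 8 patients with any SAE and on the extreme cases of none or all being attributed. The conclusion also assumes that only the named endpoint is tabulated, which the documents neither state nor rule out.

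**What to change.** In Section C, Endpoints and Statistical/Analytical Plan:

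- Make the main safety summary the number and proportion of all dosed patients with any SAE, regardless of judged cause, from first dose to week 52, with an exact 95% CI.
- Keep patients removed under Section D in the denominator, and count their SAEs for as long as they are followed.
- Report SAEs attributable to study drug as a subset in the same table, so the sponsor's endpoint is retained.

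In Section D, state that all SAEs are recorded regardless of cause. This may do no more than clarify the present wording on adverse effects.

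The cost is a few sentences and one table, plus recording of unrelated SAEs if that is not already intended. No test or visit is added.

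There are downsides. The all-cause proportion will be at least as high as the attributed one. It includes background transplant events, overlaps with death and graft loss, and does not isolate Acthar's contribution. Where a removed patient is followed for less than the full year, later SAEs will be missed, so the count is then a minimum.

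### Week-52 histology will be missing for lost grafts and for patients who die, with no rule for the gap, so describing only the available biopsies is likely to flatter the cohort

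*Combined protocol and SAP*

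**What the plan says.** Section C, Secondary end-points, item 6, lists "g and cg scores in the biopsies, maximum number of glomerular CD68+ cells", together with the severity of IF/TA. It gives no time point, comparison, analysis population or rule for a patient without tissue. Patient Monitoring and Evaluation schedules one biopsy: "patients will undergo a biopsy at week 52, as a part of our standard of care". The Statistical/Analytical Plan promises only description of the secondary endpoints by standard methods. Its one stated comparison is graft survival against a historical cohort.

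Death and graft loss (return to dialysis or retransplantation) are themselves listed endpoints. Section D adds that patients with untreatable drug-related serious adverse events, and those who do not comply, are taken off study. No biopsy is planned at graft loss or at removal. Baseline tissue is whatever biopsy gave the diagnosis, at any time after transplant.

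The design is an "open-label, uncontrolled, pilot prospective cohort study", and "We are planning to enroll 20 patients with histological diagnosis of CAMR". Section B states that glomerular CD68+ cells were the sole independent predictor of graft survival in the centre's own work.

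**The concern.** If nothing more is specified, the histology summary falls by default to the patients who have tissue at week 52. A graft that has returned to dialysis or been replaced contributes nothing. The protocol itself gives the reason to expect such grafts to be the worse ones, at least for CD68. Leaving them out then lowers the average lesion score with no drug effect, and there is no concurrent arm in which the same selection would show.

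Histology and CD68 carry the mechanistic argument for the drug. Section E foresees separate manuscripts on secondary endpoints, so these results may be read apart from the composite that counts graft loss and death. The sample size section also expects the data to inform later power calculations.

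**Working it through.** **The plan's own figure.** There is none to reproduce: "The enrollment plan is not based on power calculation", and no histology effect or expected number of biopsies is stated.

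**Inputs from the documents.** 20 patients. Mean graft survival of 43±7 months after diagnosis of transplant glomerulopathy in a cited series. For the centre's own 145 patients: "Graft survival at 66 months of diagnosis was only 10" per cent. Entry requires eGFR above 25 ml/min.

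**Assumptions.** Constant hazard from diagnosis; severity and propensity to graft loss jointly normal with correlation ρ = 0.3 to 0.7. The documents give neither.

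**Step 1: graft loss by 12 months.**
- Mean 43 months: 1 − exp(−12/43) = 24.4%, and 20 × 0.244 = 4.9 grafts. Means of 50 and 36 months give 21.3% and 28.3%.
- 10% surviving at 66 months: 1 − exp(−12 × ln 10/66) = 34.2%, or 6.8 grafts.
- If the eGFR limit selects better grafts, with loss assumed at 5-10%: 1 to 2 grafts.

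The chance that at least one of 20 grafts is lost, 1 − (1 − p)^20, is 0.64 at 5%, 0.88 at 10%, and above 0.99 at 24.4% and 34.2%. The chance of at least three is 0.90 at 24.4% and 0.99 at 34.2%.

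**Step 2: biopsies left.** About 15 (24.4% loss) or 13 (34.2%). A further 10% lost to death or removal (assumed) leaves about 14 or 12.

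**Step 3: shift in the survivor mean with no drug effect.** If the fraction p with the highest propensity is lost, the survivors' mean severity is below the cohort mean by ρ × φ(c)/(1 − p) SD, where φ is the standard normal density and c is its (1 − p) quantile.

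| Loss p | φ(c)/(1 − p) | ρ = 0.3 | ρ = 0.7 |
|---|---|---|---|
| 5% | 0.109 | 0.03 | 0.08 |
| 10% | 0.195 | 0.06 | 0.14 |
| 24.4% | 0.414 | 0.12 | 0.29 |
| 34.2% | 0.558 | 0.17 | 0.39 |

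At ρ = 0 the shift is zero.

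**Step 4: a second model on the cg scale.** Scores of 0-3 were simulated with baseline mean 1.77. An assumed 40% of patients progress by one point (capped at 3), there is no treatment effect, and the odds of loss double or triple per week-52 cg point (assumed). True mean change is +0.31.

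| Loss | Survivors' week-52 mean minus everyone's baseline | Paired change, same patients |
|---|---|---|
| 10% | +0.27 to +0.25 | +0.31 to +0.30 |
| 24.3% | +0.20 to +0.16 | +0.30 to +0.29 |
| 34.2% | +0.15 to +0.08 | +0.29 to +0.28 |

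The unpaired summary hides part of the progression. The paired one stays close to the truth in this model.

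**The case against.** The strongest reply is that the plan is silent rather than wrong. A reader might infer that it will set survivors' week-52 scores against everyone's diagnostic biopsies and so show improvement even if no graft changed. No section plans that comparison, and description could equally be by patient or paired. In the simulation even the unpaired summary shows worsening, only less of it. Apparent improvement would need both the unplanned comparison and little or no progression, in a disease that the Background describes as progressive. This part of the reply stands.

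Three further points also stand in part.
- A reader might infer that every removed patient lacks a biopsy. The documents do not say so: the week-52 biopsy is standard of care and may still be done, although the plan does not say it will be collected.
- Removal for adverse events or non-compliance, or death with a functioning graft, need not go with worse lesions. The direction of bias rests mainly on graft loss, and the Background supports it explicitly only for CD68, not for g, cg or IF/TA.
- The 24-34% loss comes from glomerulopathy series without the eGFR restriction. At 5-10% loss the shift of 0.03-0.14 SD is smaller than the standard error of a mean of 18 or 19 patients, about 0.23 SD (1/√19 = 0.229; 1/√18 = 0.236).

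It can also be said that this is a descriptive secondary endpoint in a small feasibility study, and that the primary composite already counts graft loss and death. That limits the weight of the point. It does not supply a rule for item 6.

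**Conclusion.** The concern holds as a likely bias from an unspecified rule, not as a certain one. Item 6 will lack values for grafts lost before week 52 and for patients who die, and possibly for those removed. Because the protocol ties CD68+ cells to graft survival, describing only the available biopsies is likely to flatter the cohort.

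The size is uncertain: about 0.12-0.39 SD if one-year loss follows the Background figures, and about 0.03-0.14 SD if the eGFR limit brings it to 5-10%. Both ranges rest on the assumed correlation of 0.3-0.7, and the first also on a constant hazard. The primary endpoint is unaffected. The change is worth making because it is cheap, not because the study's main result depends on it.

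**What to change.** Add to the Statistical/Analytical Plan, for item 6:

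(a) The main summary is paired change from the diagnostic to the week-52 biopsy in the same patients. Give the number biopsied out of those enrolled and the reason for each absent biopsy.

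(b) For g, cg and IF/TA, also report the proportion with no worsening out of all enrolled, counting graft loss as worsening. Use worst-rank scoring of graft loss as a sensitivity analysis only, and show death with a functioning graft separately. This covers what paired change cannot: grafts that progressed fast enough to be lost.

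(c) Include any standard-of-care week-52 biopsy from patients removed from the study. Show those without one as missing, with best-case and worst-case bounds. For example, two such patients out of 20 widen the reported proportion by 2/20 = 10 percentage points.

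(d) Report CD68 change only where the diagnostic tissue was already stained, since the protocol does not commit to staining it. Otherwise give week-52 CD68 values labelled as coming from surviving, biopsied grafts only.

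The cost is slightly more analysis and a summary that is less familiar and probably less favourable. No new biopsy or staining is needed. Diagnostic biopsies may date from any time after transplant, so the paired intervals will vary and should be stated.

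### The historical graft-survival comparison sets no eligibility rule beyond CAMR and no time zero, so a drug with no effect can appear to help

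*Combined protocol and SAP*

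**What the plan says.** The Statistical/Analytical Plan in section C gives the comparison one sentence and ranks it as secondary. It reads: "a historical cohort of patients with CAMR will be identified and graft survival in the study group will be compared with the historical cohort". The technique is left unnamed beyond being of the time-to-event kind. The plan states no eligibility rule for the historical patients other than CAMR, and no time origin, delayed-entry rule, matching or adjustment.

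The study group is defined much more tightly in the same section. Inclusion requires "eGFR>25 ml/min" and "Morphologic diagnosis of CAMR, by light &/or electron microscopy any time after transplantation". Exclusions include "Lack of evidence of antibody involvement", active infection or HIV history, and most malignancies within the prior year. No limit is placed on the time from diagnostic biopsy to enrolment.

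Two clocks appear in the document, and neither is assigned to this comparison. The primary composite is assessed "at one year after initiation of the treatment". The centre's own series of 145 patients with transplant glomerulopathy is reported from diagnosis: "Graft survival at 66 months of diagnosis was only 10" percent (Background).

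**The concern.** Three separate problems follow.

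- **(a) Unequal eligibility.** Historical patients with eGFR of 25 or less may be included. If they lose grafts faster, the study group looks better even when both groups share a clock.
- **(b) Diagnosis clock in both groups, delayed entry ignored.** A study patient must have a working graft at first dose. The wait from biopsy to first dose is then immortal time, credited to the drug.
- **(c) First-dose clock for the study group, diagnosis clock for the historical group.** The groups are compared at different stages of disease. There is no bias under constant hazard, bias against the drug if the hazard rises with time since diagnosis, and bias for it if the hazard falls.

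The Specific Aims state that the drug is "associated with improved graft outcome", and this is the only comparison that bears on that. The Sample Size Justification says the cohort is "expected to provide invaluable data regarding the treatment effect, and provide data for power calculation for future studies". A spurious hazard ratio therefore has a route into the design of a later trial.

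**Working it through.** The plan states no operating characteristic for this comparison, so there is no figure to reproduce. The check asks what each reading of the sentence does when the drug has no effect.

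**Inputs from the documents.** 20 study patients; visits to 52 weeks (12 months used); 10% graft survival at 66 months from diagnosis.

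**Assumptions.** 145 historical patients (the size of the centre's series, which the plan does not name as the comparator); share of historical patients with low eGFR and their relative hazard; wait from diagnosis to first dose; two-sided 5% log-rank test.

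**Baseline.** Constant hazard λ = ln(10)/66 = 0.0349 per month. Twelve-month survival is exp(−12 × 0.0349) = 65.8%, so about 20 × 0.342 = 6.8 losses are expected in the study group.

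**(a) Eligibility alone, common clock.** Let 30% of the historical cohort have three times the hazard of the rest, keeping 10% overall at 66 months: 0.7·exp(−66h) + 0.3·exp(−198h) = 0.10 gives h = 0.0296. Twelve-month survival is exp(−12h) = 70.1% in eligible patients and 0.7 × 0.701 + 0.3 × 0.344 = 59.4% in the unrestricted cohort. The ratio of cumulative hazards is ln(0.701)/ln(0.594) = 0.68 with no drug effect.

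**(b) Diagnosis clock, no delayed entry.** Mean time at risk in the 12 months after first dose is (1 − 0.658)/0.0349 = 9.80 months. Adding a wait of L event-free months to the denominator gives an apparent hazard ratio of 9.80/(9.80 + L): 0.77, 0.62 and 0.45 for fixed waits of 3, 6 and 12 months.

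**(c) First dose against diagnosis.** With Weibull cumulative hazard H(t) = ln(10)·(t/66)^k, historical 12-month survival is exp(−H(12)) and study survival is exp(−[H(L+12) − H(L)]). For L = 6:

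| Shape k | Historical | Study, inert drug |
|---|---|---|
| 0.7 (falling) | 49.7% | 60.8% |
| 1 (constant) | 65.8% | 65.8% |
| 1.5 (rising) | 83.7% | 76.7% |
| 2 (rising) | 92.7% | 85.9% |

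**Simulated error rates.** Exponentially distributed waits, 4,000 runs per scenario, Monte Carlo standard error at most 0.8 points. O/E is observed over expected losses in the study group; false benefit is z < −1.96 and false harm is z > 1.96.

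| Scenario, inert drug | O/E | False benefit | False harm |
|---|---|---|---|
| Unbiased reference | 1.00 | 1.5% | 3.9% |
| (a) 30% low eGFR, 3× hazard | 0.70 | 12% | |
| (a) 15–45% low eGFR, 1.5–3× hazard | 0.95–0.60 | 2–21% | |
| (b) mean wait 1, 3, 6, 12 months | 0.91, 0.79, 0.65, 0.49 | 2, 6, 17, 54% | |
| (a)+(b) 30% at 3×, 6-month wait | 0.48 | 52% | |
| (c) constant hazard, 3–12 months | 1.00–1.01 | about 1.5% | |
| (c) rising hazard, shape 1.5–2 | 1.22–2.39 | | 9–46% |
| (c) falling hazard, shape 0.7 | 0.82–0.69 | 7–15% | |

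The 17% in (b) ranges from 2% (shape 2) to 46% (shape 0.7). Combining (a) with (c), at 30% with 3× hazard and a 6-month wait, gives O/E from 0.56 to 1.20 depending on hazard shape.

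**A differently built model.** A simulation of eGFR trajectories, with waits spread over 0 to 12, 24 or 36 months, gave false benefit in 51–97% of runs on the diagnosis clock without delayed entry. Delayed entry alone, without matched eligibility, still left 15–77%. With both matched it was 0–2.4%.

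**Downstream use.** If an apparent hazard ratio of 0.70 from an inert drug were used to plan a 1:1 trial with 80% power at two-sided 5%, the Schoenfeld formula gives 4 × (1.960 + 0.842)² / (ln 0.70)² = 247 events, for an effect that does not exist.

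**The case against.** The strongest reply is one of proportion: this is an uncontrolled pilot for safety and feasibility, its endpoints are to be described, and the historical comparison is a single secondary sentence. That stands, and it is why the point is a should-fix. The primary description is unaffected.

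The sizes are also open to challenge. The low-eGFR share, its hazard and every wait are assumed. If nearly all historical patients exceed eGFR 25 and there is no wait, O/E is 0.96–0.98 and the problem all but disappears. The Background also cites a series with mean graft survival of 43 months. At a constant hazard of 1/43 per month, false benefit under (b) falls from about 18% to 11% for a 6-month wait and from about 59% to 34% for 12 months, while O/E barely moves. The (a)+(b) pairing is the unfavourable one. The only study clock in the document is treatment initiation, and pairing (a) with (c) can come out near neutral: O/E 0.95 for shape 1.5. All of this is fair. It limits how firmly any one figure can be held, but it does not supply the missing rules.

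The plan does not say that the historical hazard ratio will feed a future power calculation, so the 247 events are an example only. Nor would the fix remove differences in era or in added immunosuppression, IVIG or rituximab.

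**Conclusion.** The concern holds. The comparator is defined by CAMR alone, no time origin is given, and nothing elsewhere in the document fills either gap. Unequal eligibility favours the drug if low-eGFR patients lose grafts faster. A diagnosis clock without delayed entry favours it whenever there is a wait. Mixed clocks can favour it, be neutral or work against it. The net direction therefore depends on the clock, the length of the wait and the shape of the hazard, none of which the plan fixes.

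Confidence is high on the omission and on the possible directions of bias. The sizes are illustrative: under the assumptions above, false benefit runs from 2% to 54% for (a) or (b) taken singly, against 1.5% for an unbiased comparison. An unspecified survival method does not by itself correct this.

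**What to change.** Replace the sentence in the Statistical/Analytical Plan with rules that say:

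- Historical patients must meet the study's inclusion and exclusion criteria, as far as records allow and including eGFR above 25 and evidence of antibody involvement, at a defined index date with a functioning graft.
- Time is measured from diagnostic biopsy with delayed entry at first dose (study) or index date (historical). Alternatively, both clocks start at index dates matched on time since diagnosis.
- Follow-up is truncated at 52 weeks from index in both groups.
- These rules are fixed before historical outcomes are compared.
- The hazard ratio is reported with a 95% confidence interval and labelled hypothesis-generating, with adjustment for index eGFR if event numbers allow.

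Eligibility and clock must be fixed together. Simulated with 30% low eGFR at 3× hazard and a 6-month wait (3,000 runs), these rules gave O/E 0.98–1.00 and false benefit 0.4–1.6% across shapes 0.7 to 2. That simulation contains no other confounding.

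The cost is wording plus chart abstraction. Under the same assumptions the usable historical cohort falls from 145 to about 75–86, and the result may look less favourable. Power for a true hazard ratio of 0.5 is about 17% under constant hazard (20–22% without the eligibility restriction) and about 8% if the hazard rises (shape 1.5). Treatment, visits and enrolment do not change.
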